# 8) Procedures Involved\*

After informed consent is obtained from each subject, they will be invited to participate in the study for 3 visits over 4 weeks. The procedures involved are listed in the table of assessments.

Week	0	+2	+4
Visit	V1	V2	V4
Window (days)	0	±3	±3
Informed consent	X		
Eligibility	X		
Subject ID assignment	X		
Chart review	X		
Demographics	X		
HS history	X		
Medical history	X		
Concomitant medication	X	X	X
Physical exam (focused)	X	X	X
HS lesion map	X X X X	X X X	X
HS lesion ultrasound	X	X	X X X
Hurley stage	X	X	X
HS-PGA	X	X	X
Pain (VAS) -General	X	X	X
Pain (VAS) -target TW	X	X	X
Pain medication usage	X	X	X
past 3 days		Λ	Λ
Height	X		
Body weight	X		X
Exudate	X	X X	X
Erythema	X	X	X
Range of motion affected joint	X	X	X
Incision and drainage	X		
Product application	X	X	X
Tissue collection	X		X
Serum collection	X		X X
QOL	X		X
Work/school days lost	X	X	X
Number of dressing used	X	X	X
Photography	X	X	X
Ease of ABWG	i		
application	X	X	X
Adverse events	X	X	X

At the first visit, the medical history will be reviewed and demographics, HS history and concomitant medications will recorded using the medical chart and history given by the patient. Then, the tunnel of interest will be identified and a picture of the lesion will be taken. The first swab of the lesion will be performed and placed in a collection tube labeled with the patient number, date and "pre." The area will be cleaned, then anesthetized using local anesthesia. Once the area is properly anesthetized, a punch incision will be made and the tissue placed in a sterile petri dish lined with gauze labeled with the patient number, date and 1. After the tissue is place in the dish, sterile PBS will be added to the gauze.

A probe will then be inserted into the tunnel to identify the terminal end. A second punch incision will be made at the end of the tunnel and the tissue will be collected in a second sterile petri dish labeled with the patient number, date and 2. Hemostasis will be achieved. Once hemostasis is achieved, a second picture will be taken of the lesion. The ABWG (BlastX, NextScience, Jacksonville, FL) will then be applied to both punch sites using a tongue depressor. Absorbent dressing will be applied to cover the wound.

In the days between visits, patients will apply one fingertip unit of the ABWG to the study wound daily.

In order to correlate the change in microbiome to secondary clinical outcomes, at each visit a focused physical exam will be performed. The corresponding HS-PGA (Table 1) and Hurley Stage (Table 2) will be calculated. The HS lesion locations will be marked on a HS Lesion Body Map (Table 3) and will also be photographed using standard photography.

At each visit, the subject's pain on a 100mm visual analog scale, amount of pain medication used, number of dressings used, quality of life, and number of work/school days lost will also be quantified. Wound site exudate will be graded based on the Table 4 below. HS lesion erythema will be graded on the Clinical Erythema Assessment (CEA) scale (Table 5) at each visit. Active range of motion in degrees of the nearby joint (shoulder or hip) will be observed and recorded using a goniometer in the following directions: flexion, extension, abduction, internal and external rotation (Table 6). During the first and last visit quality of life will be assessed utilizing the Dermatology Life Quality Index (DLQI) and the HS Quality of Life Questioner (HiSQOL). The DLQI questionnaire is designed for use in adult participants with inflammatory skin diseases and has been used in HS studies. The DLQI surveys participants about symptoms and feelings, daily activities, leisure, work and school, personal relationships and treatment. The DLQI total score ranges 0 -30 (lower scores indicating higher health related QOL). A total score of 0 or 1 indicates no significant impact of the disease on health related QOL. A 4 point change in the DLQI total score has been reported to be a meaningful change in the subject's QOL. The HiSQOL questionnaire is comprised of 17 items and has a recall period of 7 days. The HiSQOL includes 3 subscales: symptom status, psychosocial impact, and impact on physical activities. It has been recently validated and is HS disease specific.

At the last visit, the lesion will be swabbed, and the sample will be collected per the tissue collection protocol above. The patient will then be offered excision of the lesion and that tissue will be collected and sent to the lab, as well.

Data and specimens can be accessed by approved study personnel only.

Table 1: HS PGA Scale

# Appendix Table 1. Hidradenitis Suppurativa Physician's Global Assessment Scale

Rating	Description
Clear	0 abscesses, 0 draining fistulas, 0 inflammatory nodules, and 0 noninflammatory nodules
Minimal	O abscesses, O draining fistulas, O inflammatory nodules, and presence of noninflammatory nodules
Mild	O abscesses, O draining fistulas, and 1–4 inflammatory nodules or 1 abscess or draining fistula and O inflammatory nodules
Moderate	0 abscesses, 0 draining fistulas, and ≥5 inflammatory nodules or 1 abscess or draining fistula and ≥1 inflammatory nodule or 2–5 abscesses or draining fistulas and <10 inflammatory nodules
Severe	2–5 abscesses or draining fistulas and ≥10 inflammatory nodules
Very severe	>5 abscesses or draining fistulas

[figure not shown]
Table 2: Hurley Score

**Stage 1** - single or multiple abscesses without sinus tract formation or scarring

**Stage 2** - recurrent abscesses with one or more sinus tracts and scarring widely separated by normal skin

**Stage 3** - diffuse involvement with multiple sinus tracts and no intervening normal skin

Table 3: Body Map

[figure not shown]

Table 4: Exudate Evaluation

	Indicators		
Status	Wound bed	Dressing	Surrounding skin
Dry	Wound bed is dry; there is no visible moisture	Primary dressing is unmarked; dressing may be adherent to wound	Skin may be scaly, atrophic, hyperkeratotic
Moist	Small amounts of fluid are visible when dressing is removed; wound bed may appear glossy	Primary dressing may be lightly marked; dressing change frequency is appropriate	Skin is likely to be intact, hydrated, no lesions
Wet	Small amounts of fluid are visible when the	Primary dressing is extensively marked, but strikethrough does not	Initial fragmented areas of

	dressing is removed	occur; appropriate dressing change frequency	maceration may be apparent
Saturate d	Free fluid is visible when the dressing is removed	Primary dressing is wet and strikethrough occurs; dressing change is required more frequently than usual	Peri-wound skin is likely to be macerated or denuded with extensive involvement
Leaking	Free fluid is visible when the dressing is removed	Dressings are saturated and exudate is escaping from primary and secondary dressings onto clothes or beyond; dressing change is required much more frequently than usual	Peri wound skin is likely to be macerated or denuded with extensive involvement

Table 5: Clinician Erythema Assessment (CEA)

	CEA
0 = Clear	Clear skin with no signs of erythema
1 = Almost clear	Almost clear; slight redness
2 = Mild	Mild erythema, definite redness
3 = Moderate	Moderate erythema; marked redness
4 = Severe	Severe erythema; fiery redness

# 9) Data and Specimen Banking\*

Study records including informed consents and source documents will be stored in a locked cabinet in the Dermatology Clinical Trials Unit at University of Miami (University of Miami Hospital West Building, [name]).

Collected samples will be assigned numeric identifiers (subject ID, visit and date of collection). Specimens will be banked for future use and kept under lock in the [name] laboratory ([name]). All specimens will be stored at -80°C in the laboratory ([name]).

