# 2) Background\*

Hidradenitis Suppurativa (HS) is a devastating chronic skin disease affecting approximately 1% of the population. Currently, there is no cure for HS. Standard care includes combination of medical and surgical therapies. There is only one agent tested in RCT which provides moderate relief to about half of the patients. As part of disease progression, dermal and subcutaneous tunneling wounds (TW) that communicate with the skin's surface form and are colonized with bacteria. Emerging evidence suggests biofilms form in the TW of HS. Tunnel formation occurs when patients go from locally contained disease to having systemic inflammatory disease and symptoms. While it is generally believed that the skin microbiome participates in the pathogenesis of HS, the presence and the role of biofilms in the cutaneous tunnels has not been well characterized. Additionally, if biofilms exist, eradication of biofilms in the TW may improve HS. We have reported our anecdotal success with treatment of HS TW with antibiofilm surfactant wound gel (ABWG,) (in submission) and we aim to prospectively examine the mechanisms involved.

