#### 7) Study Endpoints\*

The primary endpoint of the study is the change in microbiome from HS TW before and after 4 weeks treatment with the ABWG as measured by quantitative 16s rDNA PCR for bacterial enumeration.

Secondary outcomes include: Change in lesion severity (as measured by HS-PGA (Table 1) and Hurley Stage (Table 2)), change in pain from baseline (as measured by a 100 mm visual analogue scale), change from baseline in HS lesion erythema as measured by the Clinical Erythema Assessment (CEA) scale (Table 5), change from baseline in exudate graded from none to leaking (see Table 4), changes from baseline in range of motion as measured by a goniometer in the following directions: flexion, extension, abduction, internal and external rotation (Table 6), change in quantity and type of pain medication use, weekly change in number days of work/school lost, number of dressing used per week, Quality of life (using HiSQOL and DLQI).

Other descriptive measures included:

- Microbiome assessment from the tissue using metagenome shotgun sequencing approach to identify all species and their corresponding virulence factors, including genes responsible for biofilm formation antibiotic resistance genes, etc.
- Tissue assessment by histology
- Inflammatory and antimicrobial tissue response by host gene expression before and after treatment for ten representative genes.
- Confocal laser scanning microscopy to visualize and confirm biofilm before and after treatment will be performed on a small subset of subjects (about 5)
- Change from baseline in serum levels of markers of inflammation such as IL-6, IL-8, IL-10, IL-17α, soluble TNF receptor II (sTNF-RII), C-reactive protein (CRP) and erythrocyte sedimentation rate (ESR).

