#### 10) Data and Specimen Management

Data collected will be analyzed by study staff. All study data will be saved on UM computers that are password protected. After initial data collection, all data analyses will be conducted in aggregates and will be de-identified.

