# 15) Potential Benefits to Subjects\*

Regardless of the research outcomes, the patients will benefit from immediate symptom relief. They will also have better healing of the lesions. They may also experience no recurrence in the areas treated. If our hypothesis is correct, they will be spared worsening of disease. Given the poor overall management of HS nationwide, patients will benefit from

care at an expert medical center. Patients will also have access to free dressing and wound care for the duration of the study which are infrequently covered for HS.

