#### 23) Confidentiality

The research team will keep all study information and samples in a locked office and laboratory under password protection while the database is maintained. All data and specimens will be de-identified and coded as described earlier. The data will be only accessible by the research team. Local transport of study specimens will be done in a sealed biohazard bag within a secondary container with a secured lid.

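### Nothing in the protocol masks the histology or confocal reader to time point, while the sample identifier carries visit and date; re-coding slides and images would be a cheap safeguard (minor)

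*Protocol*

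**What the plan says.** - **Identifier.** Section 9 (Data and Specimen Banking): "Collected samples will be assigned numeric identifiers (subject ID, visit and date of collection". In section 8 the baseline tissue dishes are labelled with patient number, date and punch number. At the last visit tissue is collected by the same procedure.
- **Coding.** Section 23 (Confidentiality): "All data and specimens will be de-identified and coded as described earlier". Item 26(d) there keeps the link between code and subject in a separate document, and the biospecimen item after it has specimens stored coded and de-identified.
- **Access and analysis.** Section 8: "Data and specimens can be accessed by approved study personnel only". Section 10: "Data collected will be analyzed by study staff".
- **Blinding.** Section 11 calls the study unblinded, as part of the reason for having no data monitoring committee.
- **The two reads.** Section 7 lists histology and confocal microscopy among the other descriptive measures. For confocal it says: "Confocal laser scanning microscopy to visualize and confirm biofilm before and after treatment will be performed on a small subset of subjects (about 5". H2 in section 1 names histology as one of several alternative ways to determine that biofilms resolve; it does not name confocal microscopy.
- **Expected direction.** Section 2: "We have reported our anecdotal success with treatment of HS TW with antibiofilm surfactant wound gel". H2 itself states that treatment can resolve biofilms.

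**The concern.** Judging biofilm or tissue change from a slide or an image takes a human eye. There is one treatment and no comparison group, so the whole contrast is before against after. A reader who knows the time point therefore knows the treatment status of every specimen. The protocol also states which way it expects the result to go. In that setting a reader's expectation, if present, would pass straight into the before/after difference, with no control group to show it.

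The practical stake is a favourable histology read cited in support of H2, or a set of confocal images cited as showing biofilm before and less after, without assurance that the reader did not know which was which. Stored slides or images could be read again later, but assessments already made cannot be masked in retrospect, so it is cheaper to plan this beforehand.

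**Working it through.** The protocol gives no figure on this point to reproduce, and no alpha, power or effect size enters. The check is a comparison of the text, then a count of the work involved.

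**Text, side by side**

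1. Does the identifier reveal the time point? Yes. It contains visit and date (section 9), and tissue is collected only at week 0 and week 4 (section 8 schedule).
2. Does time point equal treatment status? Yes. Section 8 gives the gel to every subject after the baseline tissue is taken.
3. Does the coding remove the time point? No. Section 23, item 26(d) and the biospecimen item separate the data and specimens from the subject's identity. None of them removes visit or date.
4. Is masked or random-order reading provided elsewhere? No section mentions it for histology or confocal microscopy.
5. Is it stated that the reader sees the section 9 identifier? No. The protocol does not say what label a finished slide or image file carries, or who reads it. This link is an inference, and the concern depends on it.

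**Upper bounds on items to re-code**

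Inputs: 12 planned completers and up to 15 consented (section 22); 2 tissue visits; 2 punches at baseline (section 8); about 5 confocal subjects (section 7). Assumption: both punches are repeated at the last visit.

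Formula: items = subjects × tissue visits × punches read per visit.

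| Read | Calculation | Items | Before/after pairs |
|---|---|---|---|
| Histology, 12 completers, both punches | 12 × 2 × 2 | 48 | 24 |
| Histology, 15 complete, both punches | 15 × 2 × 2 | 60 | 30 |
| Histology, 12 completers, one punch | 12 × 2 × 1 | 24 | 12 |
| Confocal, both punches | 5 × 2 × 2 | about 20 | about 10 |
| Confocal, one punch | 5 × 2 × 1 | about 10 | about 5 |

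These are ceilings. The same tissue also serves other assays, for example "Microbiome assessment from the tissue using metagenome shotgun sequencing approach to identify all species", and its allocation to histology is not stated. Optional excision tissue is not counted; it could add up to one item per subject, so at most 15. The counts measure the size of the task, not any effect on a conclusion.

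**The case against.** The strongest case against is that the protocol contains no error here. Visit and date belong on a banking label. Section 9 governs stored samples, not slides or image files. Both reads are descriptive, with no score or test attached, and the confocal work is a visualisation in about 5 subjects. The access and analysis sentences do not identify the reader: approved personnel could include a laboratory scientist with no patient contact, and section 20 lists the laboratory separately from the clinical setting. A laboratory procedure not shown here might already mask the reading. The word unblinded in section 11 explains the lack of a monitoring committee and was not written about laboratory reads.

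Most of that stands, and it is why the point is minor and conditional. The omission still remains: the plan can be followed exactly as written with a reader who knows the time point, and H2 gives histology more weight than its descriptive listing suggests. Masking a reader is study conduct rather than an analysis rule, so it is not something one would expect to find only in an SAP. If a laboratory procedure covers it, one cross-reference settles the matter.

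Three stronger readings are tempting and are not supported:

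- **That the reads will be biased, or that the label is wrong.** The documents show neither. They do not say what the reader sees.
- **That the main result is compromised.** The primary endpoint is quantitative 16S PCR, which depends far less on a reader's judgement.
- **That section 15 reveals an expected histological result.** It does say "They will also have better healing of the lesions", but this comes in a list of benefits of taking part that opens by setting the research outcomes aside. The expected direction rests on section 2 and H2 alone.

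**Conclusion.** The point holds as a minor, conditional one. The identifier carries the time point, the study is unblinded with a single treatment, the coding protects identity only, and no section masks the histology or confocal reader. If the identifier or equivalent information reaches the reader, both before/after reads are open to expectation bias in the direction stated in section 2 and H2.

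The reach is limited to two descriptive reads: histology in at most 12 to 15 subjects and confocal in about 5. The documents give nothing from which a size of bias could be computed, and none is claimed. Masking would not make up for the lack of a comparison group. The conclusion assumes that no laboratory procedure outside the protocol already provides masked reading.

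**What to change.** Keep the collection labels as they are, for traceability. Add a short paragraph to section 8 or section 10 stating that:

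1. before reading, each histology slide and confocal image file gets a random code that omits visit and date;
2. slides and images are read in random order;
3. the key is held by an existing team member who does not read the slides or images, in a file the reader cannot open (the subject link document is not enough if the reader, as part of the team, can open it);
4. the key is released only after the reader's recorded assessments, whether scores or descriptions, are final.

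**Cost.** One re-coding step for the numbers counted above and a changed reading order. No added visit or procedure is needed, and no added reader provided that the person holding the key is not the one who reads. There is a small risk of specimen mix-up if the key is kept carelessly. Masking will be incomplete where healing at the baseline punch sites, or tissue from an excision, gives the time point away; it still removes the cue on the label.

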#### 10) Data and Specimen Management

Data collected will be analyzed by study staff. All study data will be saved on UM computers that are password protected. After initial data collection, all data analyses will be conducted in aggregates and will be de-identified.

# 11) Provisions to Monitor the Data to Ensure the Safety of Subjects\*

This study involves procedures that are within the standard care spectrum for HS. However, the safety of subjects is the primary objective of the PI and the study staff. All subjects will be evaluated for adverse events routinely at every study visit. PI and study staff will actively solicit relevant adverse events. Subjects will also be provided with contact information and encouraged to contact PI and study staff with any concern or emerging adverse event. Since this is small, unblinded study, a data monitoring committee is not required. Data recorded in the subject's CRF will be reviewed for specific adverse event including: pain, fever, chills, bleeding, burning or discomfort from product application. Since all procedures conducted are within the scope of standard care, we do not expect significant adverse events above and beyond the usual events associated with minimally invasive surgical procedure (i.e. incision and drainage). However, if a subject dies or experiences admission to the hospital due to adverse event that is involving the treatment site or any serious adverse event that is directly related to the study procedure, the PI will pause the study for assessment and decide if to continue the study.

# 12) Adverse events

Collecting Adverse Events

Study staff and PI are responsible for soliciting, recording and reporting any adverse event during the study period. In addition to unsolicited reports by subjects, the PI and study staff will open every visit by asking for any change in health or any other complaint since the last visit.

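### Delayed adverse events after the week-4 tissue collection have no solicited follow-up, because the schedule ends at that visit

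*Protocol*

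**What the plan says.** Section 6 (Study Timelines) sets participation at 4 weeks, 28 days give or take 3, with an initial, a follow-up and a final visit.

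In the section 8 table of assessments, the row "Tissue collection" is marked at weeks 0 and 4, and the adverse-event row at weeks 0, 2 and 4. Week 4 is the last column. The section 8 text describes the week-0 collection as two punch incisions under local anesthesia, one of them at the far end of the tunnel. At the last visit, "the sample will be collected per the tissue collection protocol above". Section 8 continues: "The patient will then be offered excision of the lesion and that tissue will be collected and sent to the lab".

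On safety, section 11 states: "All subjects will be evaluated for adverse events routinely at every study visit". It also says that the investigator and staff will actively solicit relevant events, and that subjects are "encouraged to contact PI and study staff with any concern or emerging adverse event". After a death or hospital admission from an event involving the treatment site, or a serious event directly related to the study procedure, "the PI will pause the study for assessment and decide if to continue the study".

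Section 12 defines the collection period: "Study staff and PI are responsible for soliciting, recording and reporting any adverse event during the study period". Besides taking unsolicited reports, staff "will open every visit by asking for any change in health or any other complaint since the last visit".

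Section 14 lists pain, bleeding, infection and abnormal scarring as risks of the surgical procedures.

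**The concern.** The last invasive study procedure falls on the last study day. The question that opens the week-4 visit looks back to week 2 and is asked before the new punches. No later visit exists at which the same question could be asked about them.

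Some of the risks in section 14 take time to appear. An infection at the punch site, or a wound that fails to close, would not be visible on the day of the procedure. After week 4 such an event reaches the study only by an unsolicited report or through clinical care.

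Two things are at stake. One is the safety of the individual subject, whose sampled site nobody is scheduled to ask about. The other is the pause rule in section 11. It is the only stopping safeguard the protocol describes, since section 11 says that no data monitoring committee is required, and it can act only on events that the investigator learns of. Enrolment is planned over one year, so an event in an early subject could bear on decisions about later ones. Whether that would happen in so small a study is speculative. The primary endpoint is not affected.

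**Working it through.** The plan gives no figure to reproduce here. The check sets the visit schedule against the timing of the procedures and the rules for collecting adverse events.

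**Inputs**
- Visit windows (table in section 8; section 6): week 2 ± 3 days, week 4 ± 3 days.
- Tissue collection: weeks 0 and 4 (section 8).
- Solicitation of adverse events: at study visits, during the study period (sections 11 and 12).
- Subjects: 12 planned completers, up to 15 consented (section 22, Local Number of Subjects).

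**Step 1: visit days**
- Second visit: 14 ± 3 = day 11 to 17.
- Last visit: 28 ± 3 = day 25 to 31.

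**Step 2: solicited follow-up after each tissue collection, per completer**

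| Tissue collection | Later visits with solicited adverse events | Days of solicited follow-up |
|---|---|---|
| Week 0 | 2 | 25 to 31 |
| Week 4 | 0 | 0 |

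Over 12 completers this is 12 × 2 = 24 solicited visits after the first collection and 12 × 0 = 0 after the second. These are counts of contacts and do not estimate harm.

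**Step 3: does the week-4 adverse-event mark close the gap?** In part. Section 11 asks for evaluation and active solicitation at every visit. The table also marks adverse events at week 0, when there is no earlier visit to look back to, so the mark plausibly covers events during the visit as well. Bleeding or pain at the week-4 sampling can therefore be recorded that day. Events that begin after the subject has left cannot.

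**Step 4: is a later contact defined elsewhere?** No. The part of section 13 on withdrawal of consent mentions follow-up after treatment in general terms, but no such follow-up is scheduled in section 6 or section 8.

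**Step 5: subjects affected**
- Lower figure: 12 completers.
- Upper figure: 12 + 3 = 15, if all three early leavers are sampled when they stop. Section 13 asks for the relevant visit 3 assessments at discontinuation. It does not say that tissue is among them, and it excuses incomplete termination procedures. The 15 is therefore an assumption.

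**The case against.** The strongest case on the other side has four parts.

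1. **The punch procedure is already observed.** The week-4 collection repeats the week-0 one, which has two solicited visits after it. The study will hold solicited safety data on this procedure, so the gap concerns individual late events and not an unknown hazard. This stands, and it limits the severity.

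2. **Reporting stays open.** Subjects have contact details and are encouraged to use them, with no end date given. Those recruited in clinic come from the same institution's dermatology practice. The consent pages are not in the copy at hand, so aftercare instructions cannot be called absent. This also stands. Section 12, however, lists unsolicited reports as an addition to active questioning, and the plan does not rely on them alone after the same punches at week 0.

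3. **The procedures are within standard care.** Sections 11 and 14 say so. That lowers the expected risk but does not explain why one collection is followed up and the other is not.

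4. **Safety is not a listed endpoint, and nothing here is contradictory.** Both are true. The point is an omission from the schedule.

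A reader might also infer more than the documents support:
- *No adverse event of the week-4 sampling can be captured.* Section 11 and the week-4 mark allow same-visit events to be recorded.
- *A study excision goes wholly unmonitored.* Excision is only offered and has no row in the schedule. The protocol does not say when it takes place or whether it is a study procedure. If it is clinical care from which tissue is collected, its follow-up may belong to that care.
- *Wound care stops at week 4.* Section 15 names free dressings and wound care during the study as a benefit. It does not say that care or contact ends afterwards.

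**Conclusion.** The point holds in a limited form. Under the plan as written, delayed events after the week-4 tissue collection have no solicited follow-up: 0 contacts and 0 days, against 2 visits over 25 to 31 days for the same procedure at week 0. This applies to each of the 12 planned completers, and to as many as 15 subjects on the assumption about early leavers.

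The conclusion rests on two readings. The last visit ends the subject's study period, as section 6 implies. The week-4 sampling repeats the punch collection, as section 8 says. It does not depend on excision.

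The effect on the trial is modest. The documents give no complication rate, so no number of missed events can be put forward, and the primary result does not change. The visit schedule and the adverse-event collection period are protocol matters, so a statistical analysis plan would not be expected to fill the gap. This is a cheap improvement of low to moderate severity.

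**What to change.** Add one scheduled safety telephone contact after each subject's last study tissue collection. An interval of 1 to 2 weeks is an assumed example, since the documents give no basis for one, and the sponsor should set it. With that example and a last visit on day 25 to 31, the call falls between day 25 + 7 = 32 and day 31 + 14 = 45. A call this early would not reliably detect abnormal scarring, so it should be aimed at earlier events.

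- In sections 6 and 12, extend participation and the adverse-event collection period to that contact, and add a row to the table in section 8.
- Ask about infection, bleeding and healing at the sampled site.
- Cover any excision done by then whose tissue is collected for the study.
- Include subjects sampled at early termination, unless they have withdrawn consent to further contact.
- Align the participation period in the consent form.

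The cost is about 12 calls, or up to 15 if early leavers are sampled, with no extra procedure. The downside is slightly longer participation and possibly a few more recorded adverse events.
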